that their participation is completely voluntary and can be ended at any time. Each session will last up to half an hour. To evaluate the acceptability and usefulness of the platform, we will also recruit up to 15 Healthy Patterns Sleep Study participants (IRB protocol # 825000) for virtual beta testing of the website. Participants will be selected if they have previously agreed to being contacted for research and if they have a computer or smartphone on which to view the website and surveys. Participants will be recruited as dyads (caregiver and person with dementia). Dyads will consent to the study staff contacting them via phone or BlueJeans and guiding them through the website and accompanying Qualtrics surveys. Qualtrics surveys will be administered before and after the viewing of the website; surveys will ask dyads for their feedback on the website and their confidence making decisions about future care. Virtual beta testing platforms will depend on the participants' ability and resources, and may include telephone, Skype, FaceTime, or BlueJeans and any internet browsers. Study staff will take notes on the reactions of dyads in order to improve the website and user experience after beta testing. When filling out the surveys, no identifiable information will be collected. The calls and/or video chats will not be recorded. Each Healthy Patterns participant within each dyad will receive \$15 via Greenphire gift cards at the end of study participation. Gift cards will be mailed to dyads. Each session will last up to an hour. Some identifiable information (name, DOB, email address, phone number, address) will be entered in the website but will not be used or recorded in the study. The website is hosted by Pantheon, which is a Penn approved hosting platform. The site is encrypted with SSL (Secure Sockets Layer) to protect participant information. Aim 3: Randomized Pilot. Setting/sample. We will conduct the pilot study in up to four Genesis facilities with diverse locations (urban, suburban, rural). We will also include at least one facility that serves mostly minority populations to test the effectiveness of the OCW-Dementia module among racially and ethnically diverse PWD. We will recruit up to 50 patients/residents and their SDMs. Eligible PWD will be receiving short- or long-term care at a participating NH, have documented moderate to severe cognitive impairment and have an identified SDM. We will exclude residents clearly exhibiting terminal decline, thereby reducing the likelihood of attrition. Study team members will work with Genesis staff to recruit dyads (Genesis residents and their family members or supportive decision-makers (SDMs) who are interested in participating in the study. Study team will read an assent script to interested SDMs, gain verbal assent and then send SDMs the study summary and copy of the assent script. After verbal assent is acquired, dyads will be assigned to the intervention group or usual care arm. At each site, up to 10 dyads will be recruited. Half of the dyads recruited at each site will receive their usual care and complete the demographics survey, COVID-19 survey and pre and post confidence in decision making surveys. The second half of dyads recruited at each site will receive the intervention as well as complete the demographics survey, COVID-19 survey and pre and post confidence in decision making surveys.

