## **Subject recruitment**

For Aim 2, Genesis staff members recruited will be those recommended by Genesis management. Additional participants will be recruited from the Healthy Patterns Sleep Study (IRB Protocol 825000) who have agreed to be contacted for future research. These participants (dyads) are persons with dementia with caregivers in the greater Philadelphia area who will have access to a smartphone or computer. We will conduct the pilot study in up to four Genesis facilities with diverse locations (urban, suburban, rural). We will also include at least one facility that serves mostly minority populations to test the effectiveness of the OCW-Dementia module among racially and ethnically diverse PWD. We will recruit up to 50 patients/residents and their SDMs. Eligible PWD will be receiving short-or long-term care at a participating NH, have documented moderate to severe cognitive impairment and have an identified SDM. We will exclude residents clearly exhibiting terminal decline, thereby reducing the likelihood of attrition. Strategies to address potential study limitations. If we are unable to rapidly recruit sufficient numbers of PWD and SDMs at up to four facilities for Aim 3, we will work with Genesis leaders to expand recruitment to additional facilities. There are 25 Genesis facilities within a 25-mile radius of the Penns campus. For Aim 3, Study team members will work with Genesis staff to recruit dyads, ie. Genesis residents and their supportive decision-makers (SDMs) who are interested in participating in the study. Study team will read an assent script to interested SDMs, gain verbal assent and then send SDMs the study summary and copy of the assent script. After verbal assent is acquired, dyads will be randomized to the intervention group or usual care arm. At each site, up to 10 dyads will be recruited. Half of the dyads recruited at each site will receive their usual care and complete the demographics survey, COVID-19 survey and pre and post confidence in decision making surveys. The second half of dyads recruited at each site will receive the intervention as well as complete the demographics survey, COVID-19 survey and pre and post confidence in decision making surveys.

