### **Analysis Plan**

We will use Z-tests to test our hypothesis that a significantly higher percentage of participants in the intervention group will complete an ACP compared with those in the usual care group. We adjust for participant characteristics due to the small sample size, but only the most important characteristics using likelihood ratio testing to avoid an overfit model. To generate new hypotheses, we will examine differences between groups with regard to demographic and clinical variables using parametric t-tests or nonparametric Wilcoxon tests (for continuous variables) and Fishers Exact tests for binary variables. To explore differences in Decisional Conflict scale scores, we will conduct a two-group independent T-test. Based on estimates derived from the Genesis EHR, we expect that 30% of PWD/SDM in the usual care arm will have a completed ACP within several weeks following admission to participating NHs. In the intervention arm, we estimate that 70% of SDMs/PWD will complete an ACP, as has been found among other OCW users (see Preliminary Studies). Enrolling 25 participants in each arm would yield 91.5% power to detect this difference of 70% vs. 30% ACP completion rate between the intervention and control groups. This calculation is based on a 1-sided Z-test with pooled variance and a significance level of 0.05.

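### Testing demographic and clinical variables between the randomised arms is a poor way to generate hypotheses, because for pre-randomisation characteristics these tests reflect chance and leave ACP completion out (minor)

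*Combined protocol and SAP*

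**What the plan says.** The Analysis Plan has four analytic elements for the randomised pilot (Aim 3).

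- The primary Z-test addresses the hypothesis that "a significantly higher percentage of participants in the intervention group will complete an ACP compared with those in the usual care group".
- That comparison is to be adjusted for a few participant characteristics, chosen by likelihood ratio testing.
- The exploratory step at issue reads "To generate new hypotheses, we will examine differences between groups with regard to demographic and clinical variables", to be done "using parametric t-tests or nonparametric Wilcoxon tests (for continuous variables) and Fishers Exact tests for binary variables".
- Decisional Conflict scores are compared in a sentence of their own, by a two-sample t-test.

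The only groups named in that section are the intervention and usual care arms. On how they are formed, Subject recruitment says "After verbal assent is acquired, dyads will be randomized to the intervention group or usual care arm". The parallel text under Design says "After verbal assent is acquired, dyads will be assigned to the intervention group or usual care arm", although it describes Aim 3 as a randomised pilot. Neither gives a randomisation method.

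The plan does not list the demographic and clinical variables, say when they are measured, give a significance level for these tests, or say what the new hypotheses would be about.

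**The concern.** A test of a baseline characteristic between randomised arms asks whether the two arms come from populations that differ in that characteristic. Randomisation has already settled this: apart from chance they do not. A small p-value is then a chance imbalance, and a large one adds nothing.

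The outcome is also absent from the calculation. A characteristic may predict ACP completion strongly or not at all, and the between-arm test behaves the same either way. If the purpose is to learn which dyads complete an ACP, or in whom the website works best, the tests cannot serve it.

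At stake is the exploratory yield of a small pilot. Chance imbalances could be reported as leads for a later trial, while the relation between characteristics and completion, which the same data could show, has no reporting plan.

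**Working it through.** **Inputs from the Analysis Plan:** 25 per arm; completion 70% against 30%; one-sided pooled Z-test at 0.05; stated power 91.5%.

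**Assumptions, not in the documents:** number of variables k (10, range 5 to 20); two-sided 5% level for the exploratory tests; independent variables; prevalence 30% or 50% for binary variables; strength of a covariate's relation to completion (log-odds 0, 1.0 or 1.5 per SD).

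**Step 1. The plan's own figure.** The plan says "Enrolling 25 participants in each arm would yield 91.5% power".

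- Normal approximation: the standard error under the null is √(2 × 0.5 × 0.5 / 25) = 0.1414, and under the alternative √(2 × 0.21 / 25) = 0.1296. Power = Φ((0.40 − 1.645 × 0.1414) / 0.1296) = Φ(1.29) = 90.2%.
- Exact binomial enumeration of the same test gives 91.5%, so the stated figure is reproduced. Nothing below changes it.

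**Step 2. Do the planned tests respond to prognosis?** 10,000 trials were simulated with 25 per arm and completion of 30% and 70% at the covariate mean (log-odds ±0.847). The covariate was standard normal and drawn independently of arm. Percentage of trials with p < 0.05:

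| Log-odds of completion per SD | t-test between arms | t-test, completers vs non-completers |
|---|---|---|
| 0 | 4.5% | 4.9% |
| 1.0 | 5.1% | 77.8% |
| 1.5 | 5.1% | 97.5% |

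The between-arm test stays at about 5% throughout. The last column pools the arms and assumes strong effects. It shows that the data can carry the information; it is not the power of the analysis proposed below.

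**Step 3. Chance of at least one spurious difference.** For k independent tests of actual size a, this is 1 − (1 − a)^k. A continuous variable is taken at a = 5%. Fisher's test is conservative: by exact enumeration at 25 per arm its actual size is 2.29% at 30% prevalence and 3.28% at 50%.

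| k | All continuous (5%) | All binary, prevalence 50% (3.28%) | All binary, prevalence 30% (2.29%) |
|---|---|---|---|
| 5 | 22.6% | 15.4% | 10.9% |
| 10 | 40.1% | 28.4% | 20.6% |
| 15 | 53.7% | 39.4% | 29.3% |
| 20 | 64.2% | 48.7% | 37.0% |

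For k = 10: 1 − 0.95^10 = 40.1%; 1 − 0.9672^10 = 28.4%; 1 − 0.9771^10 = 20.6%. A mixed list falls between these.

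**Step 4. What the alternative can deliver.** Under the plan's rates, usual care has 25 × 0.30 = 7.5 completers and the intervention arm has 25 × (1 − 0.70) = 7.5 non-completers. The smaller completion group in each arm is therefore about 7 or 8 dyads.

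**The case against.** The strongest reply is that the sentence is open to other readings. It does not use the word baseline, and it defines neither the groups nor the clinical variables. If completers and non-completers were meant, or measures taken after assignment, the criticism would fall. The second is not far-fetched: Procedures places the COVID-19 survey with the post survey, one week after usual care or website completion. But nothing in the documents names such a grouping, or a post-assignment clinical variable, for these tests. The arms remain the natural reading, and if something else was intended the sentence needs to say so.

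A reader might infer more than the documents support in four respects.

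- *That the tests fail the plan's stated purpose.* The plan says only that new hypotheses are sought. That they concern predictors of completion or benefit is an inference.
- *That every significant result must be a false positive.* This needs sound allocation and no selective loss. No randomisation method is given, one section says assigned and the other randomised, consent is documented only when surveys are administered, and the post survey comes a week later. Faulty allocation or differential loss could create real differences in the analysed sample. Even then the tests would say nothing about who completes an ACP.
- *That these tests drive the choice of covariates.* The plan uses likelihood ratio testing for that, as a separate step, and nothing links the two.
- *That the relation of characteristics to completion is wholly ignored.* The likelihood ratio step does relate them, but only to choose adjustment covariates. No reporting of those relations and no interaction or subgroup analysis is described.

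It is also fair to say that the step is labelled as hypothesis-generating, and that any replacement will have its own multiplicity and little precision. Both are accepted, and they limit the severity.

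**Conclusion.** The concern holds in a limited form. For characteristics fixed before randomisation, given sound allocation without selective loss, the planned between-arm tests reject at about their nominal level whether or not the characteristic predicts completion. They therefore cannot suggest which dyads complete an ACP or who benefits.

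The size of the false-lead problem depends on figures the plan does not give. With ten independent variables at a two-sided 5% level it is about 40% if all are continuous, and about 21% to 28% if all are binary under Fisher's test (25 per arm, prevalence 30% to 50%). The 40% should not be quoted as a general figure.

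Severity is minor. The conclusion rests on reading the groups as the randomised arms and the variables as pre-randomisation characteristics.

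**What to change.** 1. Define the groups and list the demographic and clinical variables, with the time at which each is measured.
2. Present pre-randomisation characteristics by arm descriptively (mean and SD or median and quartiles; counts and percentages), without p-values.
3. For hypothesis generation, name a short list of characteristics before the analysis is run. Relate each to ACP completion in a model or stratified comparison that accounts for arm. Show the arm difference in completion by level of the characteristic. Report estimates with 95% confidence intervals, labelled exploratory.
4. State what the hypotheses are meant to inform, for example predictors of completion or variation in the effect of the website.

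Possible wording: *Baseline characteristics will be summarised by arm without significance tests. The association of [listed characteristics] with ACP completion, accounting for arm, and the difference in completion between arms by each characteristic, will be reported as exploratory estimates with 95% confidence intervals.*

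The cost is analysis-plan wording and similar programming. No new data, visits or change in sample size is needed, so the change remains possible although Current Status of Study reports enrolment as closed. The downside is precision: with about 7 or 8 dyads in the smaller completion group per arm the intervals will be wide, and wider still if fewer than 25 per arm were enrolled. Multiplicity also remains, so no claim should rest on these estimates.

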#### **Subjects enrolled by Penn Researchers**

50

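### The 91.5% power assumes 25 dyads per arm, but four sites capped at 10 dyads each give at most 20 per arm, with power of about 81% to 83%

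*Combined protocol and SAP*

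**What the plan says.** The Analysis Plan gives one power figure for the Aim 3 randomised pilot: "Enrolling 25 participants in each arm would yield 91.5% power to detect this difference of 70% vs. 30% ACP completion rate". It names the test behind that figure: "This calculation is based on a 1-sided Z-test with pooled variance and a significance level of 0.05".

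The Design section (Aim 3) describes where the dyads come from:

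- Sites: "We will conduct the pilot study in up to four Genesis facilities with diverse locations (urban, suburban, rural".
- Cap per site: "At each site, up to 10 dyads will be recruited".
- Split: "Half of the dyads recruited at each site will receive their usual care", and the other half receive the intervention.
- Overall ceiling: "We will recruit up to 50 patients/residents and their SDMs".

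Subject recruitment repeats all four statements and adds a contingency. It opens "If we are unable to rapidly recruit sufficient numbers of PWD and SDMs at up to four facilities for Aim 3" and continues that the team will work with the nursing-home operator's leaders to extend recruitment to other facilities, of which 25 lie within 25 miles. It does not say how many would be added and does not lift the cap of 10 per site.

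The form field "Subjects enrolled by Penn Researchers" holds the value 50, without saying whether this counts dyads or individuals. Current Status of Study reports enrolment as closed.

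**The concern.** Multiplying the two site caps gives a smaller trial than the one for which power was calculated. The plan has no other power figure, so a reader will take 91.5% as the power of the four-site pilot described in the Design section. It is the power of a pilot with 10 more dyads.

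The stake is how a non-significant result is read. At 91.5% power the chance of missing a true 70% against 30% difference is 8.5%. For a four-site pilot recruited to its limit, that chance is roughly double. Someone relying on the printed figure would treat a null result as stronger evidence against the effect than the four-site design can provide.

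**Working it through.** **Inputs.** From the Analysis Plan: completion 70% (intervention) and 30% (usual care), one-sided alpha 0.05 (critical value 1.645), Z-test with pooled variance, 25 per arm. From Design and Subject recruitment: at most 4 sites, at most 10 dyads per site, half to each arm.

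**Step 1: capacity.**

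- Four full sites: 4 × 10 = 40 dyads; 40 / 2 = 20 per arm.
- Power basis: 2 × 25 = 50 dyads. Shortfall: 50 − 40 = 10 dyads, 5 per arm.
- Sites needed for 50 dyads at 10 per site: 50 / 10 = 5.

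**Step 2: reproduce the plan's figure at 25 per arm.**

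Normal approximation, with the pooled standard error under the null and the unpooled one under the alternative:

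power = Φ[(0.4 − 1.645 × SE0) / SE1], where SE0 = √(2 × 0.5 × 0.5 / n) and SE1 = √((0.7 × 0.3 + 0.3 × 0.7) / n).

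- n = 25: SE0 = √0.02 = 0.1414; SE1 = √0.0168 = 0.1296; (0.4 − 0.2326) / 0.1296 = 1.291; power = 90.2%.

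Exact enumeration: sum the binomial probabilities, under 70% and 30%, of every pair of counts for which the pooled Z statistic is at least 1.645.

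- n = 25: 91.52%, which matches the stated 91.5%. The plan's figure is therefore correct for its own inputs and probably came from this method.

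**Step 3: same test and assumptions at the four-site maximum.**

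- n = 20, approximation: SE0 = √0.025 = 0.1581; SE1 = √0.021 = 0.1449; (0.4 − 0.2601) / 0.1449 = 0.966; power = 83.3%.
- n = 20, exact: 81.1%.

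| Dyads per arm | Full sites | Exact power | Normal approximation |
|---|---|---|---|
| 25 | 5 | 91.5% | 90.2% |
| 20 | 4 | 81.1% | 83.3% |
| Loss, 25 to 20 | | 10.4 points | 6.9 points |

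The corresponding type II error goes from 100 − 91.5 = 8.5% to 100 − 81.1 = 18.9% (exact), or from 100 − 90.2 = 9.8% to 100 − 83.3 = 16.7% (approximation).

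**Step 4: why the two losses differ.** Exact power for this test does not rise smoothly with sample size, because the set of rejecting outcomes changes in jumps. Exact power is 80.7% at 17 per arm, 83.7% at 18, 80.2% at 19, 81.1% at 20, 83.8% at 21, 91.5% at 25, 92.8% at 26 and 90.9% at 27. Twenty per arm lies just after a drop and 25 lies near a peak, so the 10.4 points combine lost sample size with discreteness. The smooth approximation gives 6.9 points.

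**The case against.** The best defence is that the plan has a route to 50. The only numerical meaning it offers for a sufficient number is 25 per arm. Four full sites would fall short of that, so the expansion clause in Subject recruitment could be invoked on its own terms, and a pool of nearby facilities is named. This stands in part: a reader might infer that 25 per arm is unattainable, and the documents do not support that. However, the clause is worded as a remedy for slow recruitment, whereas under the cap of 10 a fifth site is needed even when recruitment succeeds everywhere. No section says so.

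Second, the ceiling of 50 is an upper limit and 40 respects it, and the power sentence is conditional on enrolling 25 per arm. That is right. Taken alone, the ceiling does not contradict the site caps; the conflict is between those caps and the sample size behind the stated power.

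Third, power at 20 per arm stays above 80% by either method. This also stands, so the mismatch does not by itself show that the pilot is underpowered. Those figures do assume that all four sites fill and no dyad is lost, and the power statement makes no allowance for attrition.

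Fourth, enrolment is closed and the form's counts are 15 and 7, which even added together (22) are below 40, so the site cap may never have been the binding limit. The form gives neither unit nor aim for these counts, so the achieved Aim 3 size cannot be worked out from them. Closure limits the practical consequence but leaves the reporting question open.

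Finally, a reader might infer that the chance of missing the effect is greater at every size below 20 per arm. That fails for the exact test: power at 18 per arm (83.7%) exceeds that at 20 (81.1%).

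**Conclusion.** The inconsistency is real, and its severity is minor to moderate. The site text allows at most 20 dyads per arm, while the only stated power assumes 25. Under the plan's own assumptions the four-site maximum has about 81% (exact) to 83% (normal approximation) power, a loss of about 7 to 10 points like for like.

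This rests on the plan's 70% and 30% completion rates, its one-sided pooled Z-test at 0.05, equal allocation, four full sites and complete outcome data. It does not imply an arithmetic error in the 91.5%, which reproduces at 25 per arm.

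**What to change.** Reconcile Design, Subject recruitment, the enrolment field and the Analysis Plan in one of these ways:

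1. Restate the Aim 3 maximum as 40 dyads, 20 per arm, with about 81% to 83% power for the planned test, naming the method used.
2. Keep 25 per arm, and state in the Analysis Plan that 91.5% applies only if the expansion in Subject recruitment is used to add at least a fifth site.
3. Align the stated number of sites or the per-site cap with 50 dyads.

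In each case, say whether the 50 in the enrolment field counts dyads or individuals. Because enrolment is reported closed, give the achieved number of Aim 3 dyads per arm in the report and do not interpret a null result against 91.5% power.

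The first two options change wording only and add no sites, dyads or tests. The third, if carried out and not merely described, would mean more sites or more dyads per site, which closed enrolment makes unlikely. The downside is a less favourable stated power for the four-site design, about 81% to 83% in place of 91.5%.
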